8.11. Occupational Exposure

An occupational exposure occurs when during the performance of job duties, a person (whether a healthcare professional or otherwise) gets in unplanned direct contact with the product, which may or may not lead to the occurrence of an adverse event.

An occupational exposure is reported to the drug safety unit within 24 hours of the Investigator's awareness, using the SAE Report form, regardless of whether there is an associated AE/SAE. Since the information does not pertain to a patient enrolled in the study, the information is not reported on a CRF, however a copy of the completed SAE Report form is maintained in the investigative site file.

8.12. Withdrawal Due to Adverse Events (See also Section [Patient Withdrawal](#))

Withdrawal due to AE should be distinguished from withdrawal due to other causes, according to the definition of AE noted earlier, and recorded on the appropriate AE CRF page.

When a patient withdraws because of a SAE, the SAE must be reported in accordance with the reporting requirements defined below.

8.13. Eliciting Adverse Event Information

The investigator is to report all directly observed AEs and all AEs spontaneously reported by the study patient. In addition, each study patient will be questioned about AEs.

8.14. Reporting Requirements

Each AE is to be assessed to determine if it meets the criteria for SAEs. If an SAE occurs, expedited reporting will follow local and international regulations, as appropriate.

8.14.1. Serious Adverse Event Reporting Requirements

If an SAE occurs, Pfizer is to be notified within 24 hours of investigator awareness of the event. In particular, if the SAE is fatal or life-threatening, notification to Pfizer must be made immediately, irrespective of the extent of available AE information. This time frame also applies to additional new information (follow-up) on previously forwarded SAE reports as well as to the initial and follow-up reporting of exposure during pregnancy, exposure via breastfeeding and occupational exposure cases.

In the rare event that the investigator does not become aware of the occurrence of an SAE immediately (eg, if an outpatient study patient initially seeks treatment elsewhere), the investigator is to report the event within 24 hours after learning of it and document the time of his or her first awareness of the AE.

For all SAEs, the investigator is obligated to pursue and provide information to Pfizer in accordance with the time frames for reporting specified above. In addition, an investigator may be requested by Pfizer to obtain specific additional follow-up information in an expedited fashion. This information collected for SAEs is more detailed than that captured on the AE CRF. In general, this will include a description of the AE in sufficient detail to allow for a complete medical assessment of the case and independent determination of possible causality. Information on other possible causes of the event, such as concomitant medications, vaccines, and/or illnesses, must be provided. In the case of a patient death, a summary of available autopsy findings must be submitted as soon as possible to Pfizer or its designated representative.

8.14.2. Non Serious Adverse Event Reporting Requirements

All AEs will be reported on the AE page(s) of the CRF. It should be noted that the form for collection of SAE information is not the same as the AE CRF. Where the same data are collected, the forms must be completed in a consistent manner. For example, the same AE term should be used on both forms. AEs should be reported using concise medical terminology on the CRFs as well as on the form for collection of SAE information.

8.14.3. Sponsor Reporting Requirements to Regulatory Authorities

AE reporting, including suspected unexpected serious adverse reactions, will be carried out in accordance with applicable local regulations.

9. DATA ANALYSIS/STATISTICAL METHODS

Detailed methodology for summary and statistical analyses of the data collected in this trial will be documented in a SAP, which will be maintained by Pfizer. This document may modify the plans outlined in the protocol; however, any major modifications of the primary endpoint and/or its analysis will also be reflected in a protocol amendment.

9.1. Analysis sets

1. Full analysis set.

The full analysis set includes all enrolled patients.

2. Safety analysis set.

The safety analysis set includes all enrolled patients who receive at least one dose of study medication.

3. DLT evaluable set.

All enrolled patients who are eligible for the study and receive study treatment. Note that every patient will contribute to the determination of the MTD including patients who are lost to follow-up prior to completion of the 2 cycles' DLT observation period.

4. PK/Immunogenicity and PK parameter analysis sets.

The PK/ADA concentration population is defined as all enrolled patients who have been treated and have at least one post dose concentration measurement of either PF-05082566 or mogamulizumab.

The PK parameter analysis population is defined as all enrolled patients who have been treated and whose concentration-time data allows the estimation of at least 1 of the PK parameters of interest.

5. **CCI**

6. ECG/QTc Analysis set.

Treated patients who have baseline and at least 1 on study ECG/QTc measurement.

9.2. Statistical Methods for Dose Allocation: TITE-CRM

A number of alternative designs have been proposed to the standard 3+3 design for Phase I dose escalation trials that improve its accuracy, efficiency and statistical validity, including the continual reassessment method (CRM)^[30] and its variants.

Delayed-onset toxicities are a particular challenge for phase I trials of combination therapies.^[31] Most of the available dose-escalation designs, including the 3+3 design, the up-and-down designs and the CRM design, require all patients to have completed a fixed observation period for toxicity (eg, 1-2 cycles of the experiment regimen, or 6-8 weeks after start of treatment) before additional cohorts of patients can be enrolled. Thus, trial accrual is patient to opening and closing which may pose logistical risk on the success and completion of the study. In addition, patients who are either lost to follow-up or die of events unrelated to treatment are usually required to be replaced. Due to these reasons, the trial duration could be unacceptably long in case of prolonged observation window and unexpected high rate of patient drop-out.

The time-to-event continual reassessment method (TITE-CRM), a variant of the original CRM method, is open to accrual continually, and maintains other advantages of the CRM relative to the 3+3 design. Like CRM, TITE-CRM seeks to determine the target MTD dose, defined as the dose most closely identified with the target rate, which is the largest acceptable DLT rate determined by the investigators based on the relative costs and benefits of the treatment.

TITE-CRM is to be implemented as described by Cheung et al.^[28] and Huang et al.^[33] for the dose-escalation and de-escalation of PF-05082566. PF-05082566 may be administered intravenously at the following available dose levels of 1.2, 2.4, 100 mg flat dose (equivalent to the 1.2 mg/kg) and 5.0 mg/kg on an every 4 week schedule (q4wk).

[figure not shown]
PF-05082566 will be co-administered with mogamulizumab on Day 1 of each treatment cycle. Mogamulizumab will be administered at 1 mg/kg, weekly on Cycle 1, biweekly from Cycle 2 onwards. A lower mogamulizumab dose of 0.5 mg/kg may be tested if the starting dose is not tolerable. Different doses and different dosing schedules of the combination may be investigated after the MTD is estimated. The MTD is defined as highest dose that is associated with a DLT rate <30%. A power function modeling DLT rate at each dose d_i ($i=1, \dots, 4$) expressed as $\text{Pr}(\text{DLT} | d_i) = F_i(\beta)$ will be used:

$$F_i(\beta) = p_i^{\exp(\beta)}$$

where p_i is the prior estimate of DLT rate at dose level d_i , and $p_1 \leq p_2 \leq \dots \leq p_4$. These estimates will be projected based model sensitivity to DLTs, together with single agent safety data for both study drugs. β is an unknown single parameter modeling the dose-toxicity relationship, with prior distribution $N(0, \sigma_0^2)$, where σ_0 is the standard deviation of the normal prior distribution with mean=0. At the beginning of the trial, the initial prior value of β is set as 0, the prior mean, which gives a prior dose-toxicity model of $F_i(\beta) = p_i$ based on the power function.

In the Bayesian paradigm, the prior distribution $N(0, \sigma_0^2)$ expresses the researchers' belief in the quality of the initial estimates p_i . The smaller the standard deviation σ_0 , the more confidence researchers have in the precision of p_i , and vice versa. As the trial progresses, this prior distribution is combined mathematically with the observed data to yield the posterior distribution of the parameter β (the posterior mean of β will be calculated to model the dose-toxicity relationship). The prior distribution determines how responsive TITE-CRM is to the accumulated data. With a small σ_0 upfront, the posterior toxicity probability estimates remain close to the prior estimates unless significantly discrepant data otherwise occur; with a large σ_0 , the model will tend to be more immediately responsive to data. In this trial, $\sigma_0=1$, which provides a reasonably flat prior distribution of β , with 90% Bayesian credible interval of $\exp(\beta) : [0.19, 5.21]$, sufficiently wide to cover a wide spectrum of dose-toxicity scenarios. [Figure 3](#) illustrates the dose-toxicity curve (blue curve) with 90% upper and lower bounds (red curves) when the initial prior estimates p_i are (0.095, 0.186, 0.300, 0.422).

Figure 3. Example Plot of Prior Dose Toxicity Curve

In the TITE-CRM paradigm, patients who have enrolled in the trial but have not experienced a DLT will be included in the probability calculation with an initial weight equal to the proportion of the 8-week (2 cycles) DLT observation period the patients have completed. However the weight function will be modified if safety data suggest different weight (toxicity) patterns in Cycle 1 and Cycle 2 of PF-05082566. An adaptive cyclical weight function as proposed by Huang et al.[³³] will be implemented.

Patients who experience a DLT or complete the observation period without a DLT will be assigned full weight (=1).

Extensive simulation results comparing the TITE-CRM using the adaptive cyclical weight function with the 3+3 design and other weight functions can be found in Huang et al.[³³]

9.2.1. Statistical Methods for Dose Escalation/De-Escalation

Section 3.1.9 describes the dose escalation/de-escalation criteria, stopping rules and some restrictions and practical considerations on dose escalation.

9.3. Sample Size Determination

Due to the dynamic nature of the Bayesian allocation procedure, the sample size of the TITE-CRM approach cannot be determined in advance. The maximum sample size is set as 30 for dose escalation cohorts in order to have a reliable and accurate estimate of the MTD based on simulation results. Based on probability theory, a sample size of 30 will ensure the estimates of any binary variable (eg, objective response rate) have a 95% confidence interval of width <0.36. A sample size of 30 also enables the detection of any unexpected toxicity that occurs at 5% rate (in a non-dose-dependent fashion) with a probability of 0.79, and that occurs at 10% rate with a probability of 0.96.

A stopping rule (see [Section 3.1.9](#)) will also be implemented for possible early stopping if there is strong confidence in the estimated MTD.

Additional patients will be required for expansion cohorts. The total number of patients in expansion cohorts will be determined based on emerging data from this study, cancer indication, and the patient population of interest.

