3.1.9. Criteria for Dose Escalation

No dose escalation of mogamulizumab is foreseen for the estimation of the combination MTD. Dose escalation and de-escalation of PF-05082566 will follow the Time-to-Event Continual Reassessment Method (TITE-CRM)^[28,33] up to 5 mg/kg.

A flat dosing of PF-05082566 100 mg will be studied to confirm the safety and PK at a dose that may be used for the expansion cohorts. The safety data at 100 mg flat dose (equivalent to 1.2 mg/kg) will be pooled together with the data at 1.2 mg/kg in the TITE-CRM model.

The 5.0 mg/kg cohort (if safe and tolerable) will enroll at least 6 squamous NSCLC patients to determine RP2D.

In each cohort, 3 to 9 patients evaluable for MTD determination may be enrolled.

The first 3 patients (Dose Level 1) will be treated at the starting dose. For each subsequent patient, the probability of DLT is estimated for each level based on all the collected data from all treated patients up to that time and the prior expectations of toxicity, and the patient is assigned to the currently estimated target level (with escalation restrictions as indicated below), defined as the dose having an estimated probability of DLT closest to but not greater than the target rate (30%).

The probabilities of toxicity are estimated based on a Bayesian statistical model to learn about the overall dose-toxicity relationship.

Patients' DLT data will be reported to the study statistician who will update the dose-toxicity model before the next enrolled patient is treated.

The MTD is defined as the highest combination dose with a DLT rate <30% from the model estimate (see [Section 9.2](#)).

Dose escalation may stop if:

- Maximum sample size (n=30, see [Section 9.2](#)) is reached; or
- 9 DLT evaluable patients have been treated at the estimated MTD (6 if no DLT observed at any dose); or
- All doses appear to be overly toxic and the MTD cannot be determined in the current trial.

In the TITE-CRM paradigm, patients who have enrolled in the trial, but have not experienced DLT, will be included in the probability calculation with an initial weight equal to the proportion of the 8-week (2 cycles of PF-05082566 and mogamulizumab) DLT observation period that the patients have completed (however, the weight function may be modified if accumulating safety data suggest a different pattern).

Patients who experience DLT or complete the observation period without DLT will be assigned full weight (=1).

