3.5. Dose Expansion Portion

Expansion cohort(s) will test PF-05082566 in combination with mogamulizumab in patients with select advanced solid tumors. Tumor types for the expansion cohorts will be selected from CRC, bladder, ovarian, squamous esophageal, SCCHN and/or squamous NSCLC. The PF-05082566 dose for expansion cohorts may be a flat dose of 100 mg. All patients in the expansion cohorts may be enrolled simultaneously. The total number of patients enrolled

into one or more expansion cohorts will be determined based on the tumor type, and patient population emerging data from this study. PK/ADA samples will be collected from all evaluable patients in the dose expansion cohorts.

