5. GENERAL METHODOLOGY AND CONVENTIONS

5.1. Hypotheses and Decision Rules

5.1.1. Hypotheses and Sample Size Determination

No formal statistical hypothesis testing is planned.

Due to the dynamic nature of the Bayesian allocation procedure, the sample size of the TITE-CRM approach cannot be determined in advance. The maximum sample size is set as 30 for dose escalation cohorts in order to have a reliable and accurate estimate of the MTD based on simulation results. Based on probability theory, a sample size of 30 will ensure the estimates of any binary variable (eg, objective response rate) have a 95% confidence interval (CI) with width <0.36. A sample size of 30 also enables the detection of any unexpected toxicity that occurs at 5% rate (in a non-dose-dependent fashion) with a probability of 0.79, and that occurs at 10% rate with a probability of 0.96.

A stopping rule will also be implemented if:

- Maximum sample size (n=30) is reached; or
- 9 DLT evaluable patients have been treated at the estimated MTD (6 if no DLT observed at any dose); or
- All doses appear to be overly toxic and the MTD cannot be determined in the current trial.

Additional patients will be required for expansion cohorts (N=40). The total number of patients in expansion cohorts will be determined based on emerging data from this study, cancer indication, and the patient population of interest.

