5.2. General Methods

As described in [Section 3.4](#), in this study ‘**treatment group**’ refers to one of the following:

- Dose Level -1: PF-05082566 1.2 mg/kg q4wks + mogamulizumab 0.5 mg/kg;
- Dose Level 1: PF-05082566 1.2 mg/kg q4wks + mogamulizumab 1 mg/kg;
- Dose Level 1a: PF-05082566 100 mg q4wks + mogamulizumab 1 mg/kg;
- Dose Level 2: PF-05082566 2.4 mg/kg q4wks + mogamulizumab 1 mg/kg;
- Dose Level 3: PF-05082566 5 mg/kg q4wks + mogamulizumab 1 mg/kg.

Baseline characteristics, disposition and efficacy data will be summarized based on the FAS by treatment group.

DLTs will be summarized based on the DLT-evaluable set by treatment group.

Other safety data, exposure data, concomitant medications and non-drug treatments will be summarized based on the safety analysis set by treatment group.

PK data will be summarized based on the PK analysis sets by treatment group.

CCI

Immunogenicity data will be summarized based on the immunogenicity analysis set by treatment group.

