6.2.2.1. Objective Response as Assessed by the Investigator per RECIST v1.1

The following analyses will be based on the FAS by treatment group. Assessment of response will be made using RECIST v1.1.

Best Overall Response (BOR) will be assessed based on reported overall lesion responses at different evaluation time points from the first dose of study treatment until the first documentation of PD, according to the following rules:

- CR = at least two determinations of CR at least 4 weeks apart and before first documentation of PD.
- PR = at least two determinations of PR or better at least 4 weeks apart and before first documentation of PD (and not qualifying for a CR).
- SD (applicable only to patients with measurable disease at baseline) = at least one SD assessment (or better) ≥ 6 weeks after the first dose of study treatment and before first documentation of PD (and not qualifying for CR or PR).
- Non-CR/non-PD (applicable only to patients with non-measurable disease at baseline) = at least one non-CR/non-PD assessment (or better) ≥ 6 weeks after the first dose of study treatment and before first documentation of PD (and not qualifying for CR or PR).

- PD = progression \leq 12 weeks after the first dose of study treatment (and not qualifying for CR, PR, SD or non-CR/non-PD).
- NE: all other cases.

Only tumor assessments performed on or before the start of any further anti-cancer therapies will be considered in the assessment of BOR. Clinical deterioration will not be considered as documentation of disease progression.

Objective Response (OR) is defined as BOR of CR or PR according to RECIST v1.1

Patients who do not have a post-baseline radiographic tumor assessment (including due to early clinical progression), who receive anti-cancer therapies other than the study treatments prior to reaching a CR or PR, or who die, progress, or drop out for any reason prior to reaching a CR or PR will be counted as non-responders in the assessment of OR. Each patient will have an objective response status (0: no OR; 1: OR). OR rate (ORR) is the proportion of patients with OR in the analysis set.

ORR by treatment group will also be calculated along with the 2-sided 95% CI using the Clopper-Pearson method (exact CI for a binomial proportion as computed by default by the FREQ procedure using the EXACT option).

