^a However if the patient dies \leq xx weeks after the first dose of study treatment the death is an event with date on death date

^b irPD is also considered to be confirmed if the patient dies within 12 weeks after the initial documentation of irPD

^c If there are no adequate post-baseline assessments prior to irPD or death, then the time without adequate assessment should be measured from the first dose of study treatment; if the criteria were met the censoring will be on the first dose of study treatment.

The analyses for irBOR, irOR, irDR, irTTR will follow the methodology outlined for the RECIST v1.1 endpoints as follows:

- irOR will be summarized as described in [Section 6.2.2.1](#) for OR and 95% CIs will be reported.
- irBOR, irDR, irTTR and irPFS will be summarized by treatment group as described in [Sections 6.2.2.1, 6.2.2.3, 6.2.2.4, and 6.2.2.5](#) but irDR and irPFS will be analyzed using the censoring rules described in [Table 6](#).

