6.4. Subset Analyses

The number of patients expected in each treatment group is small and therefore no subset analyses are planned in this study.

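### The 95% CI width of <0.36 promised at n=30 holds for a normal-approximation interval but not for the Clopper-Pearson interval the SAP prescribes for ORR (minor)

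*Protocol*

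**What the plan says.** Protocol 9.3 sets 30 as the maximum for the dose-escalation cohorts and states that this number "will ensure the estimates of any binary variable (eg, objective response rate) have a 95% confidence interval of width <0.36". SAP 5.1.1 carries the same claim: "eg, objective response rate) have a 95% confidence interval (CI) with width <0.36". Neither section says which interval the width refers to.

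The method for the named example appears later. SAP 6.2.2.1 states: "ORR by treatment group will also be calculated along with the 2-sided 95% CI using the Clopper-Pearson method". SAP 6.3.1 routes the immune-related response to the same place ("irOR will be summarized as described in" section 6.2.2.1, with 95% CIs).

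The reporting unit is the treatment group. SAP 5.2 says "Baseline characteristics, disposition and efficacy data will be summarized based on the FAS by treatment group". Protocol 3.1.9 says of the dose-finding cohorts: "In each cohort, 3 to 9 patients evaluable for MTD determination may be enrolled".

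**The concern.** The sample-size text gives an unconditional guarantee: it covers every binary variable and every outcome, and it names ORR. The SAP then fixes an interval for ORR that is conservative by construction and usually wider than the normal-approximation interval. If the exact interval at n=30 can exceed 0.36, the guarantee fails for its own example under the plan's own method.

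What is at stake is whether the stated precision is accurate. A reader of the sample-size section would expect slightly tighter intervals than the prescribed method can guarantee.

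**Working it through.** **Inputs.** n = 30, 95% confidence and bound <0.36 (Protocol 9.3, SAP 5.1.1). Two-sided Clopper-Pearson interval for ORR (SAP 6.2.2.1).

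**Step 1: reproduce the stated figure.** The Wald width is 2 × 1.96 × √(p(1−p)/n), which is largest at p = 0.5:

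2 × 1.96 × √(0.25/30) = 0.358, below 0.36.

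The figure reproduces. Other methods also satisfy it at n=30: the maximum width is 0.337 for Wilson and for Agresti-Coull, and 0.344 for Jeffreys. The bound is therefore consistent with Wald, but the documents do not establish which method produced it.

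**Step 2: apply the prescribed method.** For x responders of n, the lower limit is the 0.025 quantile of Beta(x, n−x+1) and the upper limit is the 0.975 quantile of Beta(x+1, n−x). With n=30:

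| Responders | Exact 95% CI | Width |
|---|---|---|
| 5 | 0.0564 to 0.3472 | 0.291 |
| 10 | 0.1729 to 0.5281 | 0.355 |
| 11 | 0.1993 to 0.5614 | 0.362 |
| 12 | 0.2266 to 0.5940 | 0.367 |
| 13 | 0.2546 to 0.6257 | 0.371 |
| 14 | 0.2834 to 0.6567 | 0.373 |
| 15 | 0.3130 to 0.6870 | 0.374 |
| 19 | 0.4386 to 0.8007 | 0.362 |
| 20 | 0.4719 to 0.8271 | 0.355 |

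Widths are symmetric about 15. Over all x from 0 to 30, the width exceeds 0.36 for exactly x = 11 to 19. The maximum is 0.3741, so the excess is 0.3741 − 0.36 = 0.014.

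**Step 3: find what would hold.** At n=30 the bound that covers every outcome under the exact method is <0.375. To keep <0.36 for every outcome would need 33 patients (maximum 0.357; n=32 gives 0.362).

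**Step 4: look at the groups in which ORR is reported.** The maximum exact width is 0.897 at n=3, 0.764 at n=6 and 0.651 at n=9. It is 0.324 at n=40, the cap on total expansion enrolment. These are context for the n=30 figure and do not contradict it.

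**Step 5: check the neighbouring figures.** The chance of at least one event in 30 is 1 − 0.95³⁰ = 0.785 at a 5% rate and 1 − 0.90³⁰ = 0.958 at a 10% rate. Both agree with the stated 0.79 and 0.96.

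**The case against.** The strongest reply is that <0.36 is right. It is a planning figure, the usual planning formula gives 0.358, and the sentence names no method. That stands, and it means this is not a calculation mistake. It does not rescue the wording, because the text promises the width for any binary variable and names ORR, for which the SAP chose a different interval.

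A second reply is that the conflict is largely hypothetical. The 30 is a pooled maximum, whereas the Clopper-Pearson interval is attached to treatment groups. This also stands. A reader might infer that the SAP will report an ORR interval on 30 patients that breaks the promise, but no section plans an exact interval on the pooled 30. A single group could approach that size only if expansion patients joined a dose level, which Protocol 3.5 leaves open ("The PF-05082566 dose for expansion cohorts may be a flat dose of 100 mg").

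A reader might also infer that the small groups contradict the n=30 statement. They do not. The statement is conditional on 30 patients, and SAP 6.4 is open about group size: "The number of patients expected in each treatment group is small and therefore no subset analyses are planned in this study".

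A third reply is that 11 to 19 responders of 30 is unlikely. That depends on the true rate, which the documents do not forecast. Taking rates as assumptions, the binomial probability of 11 to 19 responders is 0.5% at 16%, 2.6% at 20%, 11% at 25%, 27% at 30% and 58% at 37%. The end values, 16% and 37%, are the range Protocol 1.2.6 cites for single agents in immunoresponsive tumours, which is not a prediction for this population. Even at 37% the expected exact width is 0.357. The reply supports low materiality, but a guarantee for every outcome still fails.

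**Conclusion.** The point holds as a minor mismatch between stated precision and prescribed method. Under the interval SAP 6.2.2.1 specifies, n=30 ensures a width below 0.375, not below 0.36. The bound fails for 9 of the 31 possible outcomes, by at most 0.014. The demonstrated mismatch covers ORR and irOR; for other binary variables it depends on which interval is used.

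The conclusion assumes that the sample-size sentence is read with the method the SAP prescribes for its example. Read with a normal-approximation interval, the sentence is correct.

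It would be tempting to conclude that the sample size is inadequate or should rise to 33. The documents do not support that. The limit of 30 is justified by MTD estimation through simulation, SAP 5.1.1 plans no hypothesis test, Protocol 9.4 makes efficacy descriptive, and no stopping rule or dose decision uses the width.

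**What to change.** In SAP 5.1.1, replace the <0.36 bound with: <0.375 (exact Clopper-Pearson interval; maximum 0.374 at 15 of 30). Add a note that this supersedes the protocol's <0.36, which holds for a normal-approximation interval, so that the two documents do not appear to conflict in the interim. Make the same replacement in Protocol 9.3 at its next amendment; the point does not justify an amendment of its own, since Protocol 12.1 requires prior ethics approval.

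A sentence giving the by-group widths from step 4 would be helpful but is optional. Labelling the existing figure as a normal approximation would also make it correct, with no number changed, but the stated precision would then still refer to a different interval from the one reported for ORR.

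Leave the sample size, the analysis method and the detection probabilities of 0.79 and 0.96 unchanged. The cost is a slightly less favourable stated precision and a temporary difference in wording between SAP and protocol, which SAP section 2 permits because the SAP may modify protocol plans and this does not touch the primary endpoint.
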